### 3.4 Changes in the conduct of the study compared to the protocol

The key compliance/adherence measure during the study is 24-hour urine measurement of volume and osmolality. After the start of study treatment at V3, 24-hour urine is collected at V4 (3 weeks), V5 (3 months), V6 (6 months), V7 (9 months) and V8 (12 months). Apart from the main “intention to treat” analysis, we will perform “per protocol” analysis in which we exclude subjects with major protocol deviations (i.e. whose values of 24-hour urine displays major deviation from expected, given treatment assignment, with those limits defined below (see protocol deviations)).

## 4 Analysis sets

### 4.1 Analysis sets

#### -Included subjects

Urine collection over 24 hours is collected from participants in previous population studies and from subjects living within the greater Malmö area who respond to advertising. The analysis set is the number of subjects who fulfill all inclusion criteria (including urine volume, osmolality and plasma copeptin) and are randomized to treatment allocation after V2.

At the following “baseline visit” (V3), baseline fasting metabolic measurements are done and after the baseline visit (V3), the actual active and control treatment commence. This design is the only one practically possible as study subjects need to perform the baseline measurements in the morning in the fasted state. However, of the subjects included and randomized to treatment allocation at V2 some are expected to not come to the V3 fasting baseline examination and thus never commence active or control treatment. Furthermore, of all subjects starting intervention after V3, we will probably observe a dropout during the study.

#### Intention to treat

The “Intention-to-Treat” population: all randomized study subjects with at least two during study fasting plasma glucose measurements will be analyzed in intention to treat analysis (i.e. regardless of any protocol deviations). This analysis set includes the evaluation of primary and secondary outcomes as well as adverse events (AE) and serious adverse events (SAE) between intervention and control group.

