Fluid and dietary intakes will be assessed using “*Riksmaten 2010*”, a web-based 4-day record tool developed by the Swedish National Food Administration and used in the latest national diet survey in Swedish adults. In addition to Riksmaten recording, participants will fill in a food propensity questionnaire to assess foods that may not be consumed within the 4 days (like fish, berries or sugar-sweetened beverages). To help with the registration participants will receive a food/drink dairy and a portion guide with pictures of 24 different food categories. In addition, there is an instruction video available via YouTube <https://www.youtube.com/watch?v=DB3bzD0FJMg>. The method has been validated (Nybacka et al, J Nutr Sci 2016; 5:e39).

A check for adverse events will be done at every visit after baseline and during each telephone contact by asking all participants if it has occurred any new or worsened health problems or any medical treatment or hospitalization since last contact (see section “safety reporting” below).

Participation in the present study, starting from Visit 1 until 12-month follow-up Visit, will not last longer than 18 months.

Handling of blood samples: The amount of blood drawn is 3 ml at visit 1, 61 ml at baseline visit, 6 ml at 3-week, 3-month and 9-month visits, and finally 57 ml at the 6 and 12 months visits. This includes blood for direct analyses of routine chemistry (TABLE 1) as well as backup samples (biobank samples) corresponding to 16 x 250 µl vials of EDTA plasma, 8 x 250 µl vials of citrate plasma, and 8 x 250 µl vials of serum at baseline, 6 months and 12 months. Note that in contrast to routine chemistry, copeptin will not be measured continuously during the trial but in back-up samples (one batch) after all study subjects have completed the 12-month protocol.

The buffy-coat of one of the centrifuged plasma tubes will be collected and stored frozen for later DNA extraction. We are planning to genotype genes coding for AVP and its receptors, loci associated with urine and plasma osmolality and genes associated with altered copeptin concentration.

The routine (directly analyzed) blood/urine samples are transported in air temperature from the clinical site to the University Hospital's central clinical lab by site staff. The lab is located in the area of Skane University Hospital Malmö, only a 3 minute-walk from the clinical site, which is located at [name], Skåne University Hospital, Malmö.

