The signature of the study informed consent form marks the inclusion of the subject in the study. This signature will be obtained after having fully briefed the subject about the study and answered all of his/her questions about the study.

Safety reporting: The following variables will be followed at each visit in order to assess safety measurements: serum creatine, serum osmolality and serum sodium to control for water balance problem.

Definition and registration of adverse events: An adverse event (AE) is defined as any untoward medical occurrence in a participant who is administered an investigational product. The medical occurrence does not necessarily have to have a causal relationship with the treatment. An AE can therefore be any unfavorable and unintended sign (including an abnormal laboratory finding, symptom, or disease temporally associated with the use of an investigational product, whether or not related to the investigational product.

AEs are defined as either a laboratory measurement outside the reference range (i.e. a value outside the reference values) or signs or symptoms reported by the participants during regular follow-up contacts (telephone calls and visits). During these contacts the participants will be asked if it has occurred any new or worsened health problems or any medical treatment or hospitalization since the last contact. AEs are documented in the eCRF. We will specifically ask about pregnancy, lactation and new use or change of medication.

AEs are categorized as serious (SAEs) if they result in death, illness requiring hospitalization, events deemed life-threatening, or if they result in persistent or significant disability/incapacity, or in a congenital anomaly/birth defect or medically important condition. SAEs will be reported to the sponsor within 24 hours, as well as recorded in the eCRF (V-CMS). The sponsor will report all SAEs to Danone Research within 3 days. The Adverse Event Form will be sent by email/fax to the following contact:

Position(*)	Name	Cell Phone	Email
Clinical Operations Leader	[name]	[contact]	[contact]
Hydration Physiology and Metabolism Junior Scientist	[name]	[contact]	[contact]

Registration of AEs will start with the 1st telephone contact (which is the first follow up after start of treatment). The registration of AEs ends at the 12-month visit (end of treatment).

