### 3.3 Sample size

The primary outcome parameter is the difference between active (=extra water) and control treatment in the change of fasting plasma glucose between baseline and 12 months. We use prior effect estimates from the largest RCT for diabetes prevention study in Europe, i.e. the Finnish Diabetes Prevention Study (FDPS) (New Engl J Med 2001;344:1343-50), which compared individual life style counselling (active treatment) with general oral and written life-style advice (control treatment) in relation to risk of new onset type 2 diabetes and change of plasma glucose concentration and found a 58% decreased relative risk of diabetes. After 12 months, the fasting glucose in the active treatment group was reduced by  $4 \pm 12$  mg/dL vs a  $1 \pm 12$  mg/dL increase in the control group with the mean difference of 5 mg/dL of the 12-month change of fasting glucose being highly significant ( $P < 0.001$ ).

To obtain sufficient statistical power to detect a clinically significant effect size, we base the power calculation on an effect of water vs control that is at least 50% of what is considered an epoch changing effect of lifestyle i.e., the difference observed in the FDPS, while assuming the standard deviation for the change ( $s = 0.67$  mmol/L) as observed in FDPS. To be able to detect  $\geq 50\%$  of that effect (a difference of 2.5 mg/dL = 0.14 mmol/L between treatments in 12-month change) we need 319 evaluable subjects in both the active and control treatment group at a power of 80% and a 2-tailed significance level of =0.05, a total of 638 evaluable subjects. As the glucose measurement in the study used a more recent and exact method, the standard deviation of the change of glucose was recalculated by the DSMB in October 2022 from the first completed 357 study participants ( $s = 0.58$  mmol/L). With this smaller standard deviation, the power (with all other assumptions unchanged) was 270 evaluable subjects per group, i.e.  $n=540$  evaluable subjects in total. When also taking into account a dysbalance (with slightly higher drop-out rate in subjects in the intervention group), a total of 544 evaluable subjects were estimated to be needed for 80% power.

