## Analysis of safety

### 5.7.3 Adverse events

See section “*Definition and registration of adverse events*” of the protocol. AE and SAE will be reported for all subjects who attended baseline exam and commenced study treatment (i.e. attended V3). AE and SAE will be reported as a diagnosis code (<http://icd.internetmedicin.se/>) associated with the AE/SAE, and the incidence of AE and SAE will be compared between treatment groups (intervention vs control).

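### The SAP names two different sets for comparing adverse events, and its only check on departures from missing at random is left post-hoc and unspecified

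*SAP*

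**What the plan says.** **Adverse events.** SAP section 4.1 (Intention to treat) states that "all randomized study subjects with at least two during study fasting plasma glucose measurements will be analyzed in intention to treat analysis". Section 5.1.3 explains that this means a value at V3 plus one at V6 (6 months) or V8 (12 months). The same paragraph of section 4.1 continues: "This analysis set includes the evaluation of primary and secondary outcomes as well as adverse events (AE) and serious adverse events (SAE", compared between the arms. Section 5.7.3 gives a different population: "AE and SAE will be reported for all subjects who attended baseline exam and commenced study treatment (i.e. attended V3". Its next sentence compares incidence between arms and names no other set.

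**When events are collected.** In the Protocol, "Registration of AEs will start with the 1st telephone contact", and "A check for adverse events will be done at every visit after baseline and during each telephone contact". Table 1 places checks at 3 weeks and 3 months, both before V6. On content, "AEs are defined as either a laboratory measurement outside the reference range" or reported signs and symptoms. The variables followed at each visit for safety are "serum creatine, serum osmolality and serum sodium to control for water balance problem".

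**Drop-out.** SAP section 3.3 allows for imbalance "with slightly higher drop-out rate in subjects in the intervention group". Section 5.1.3 expects the final sample to be 46% intervention and 54% control. Section 6.3 describes losses between V2 and V3 as balanced.

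**Missing outcomes.** Section 5.6.2 rests the mixed model on missing at random. Section 4.1 (Missing data) rules out imputing outcomes; chained-equation imputation there and in section 6.3 is for covariates only. The second paragraph of section 6.3 announces re-analysis with unobserved values filled under scenarios of varying pessimism, and labels this post-hoc and experimental.

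**Drop-out table.** Section 5.8 asks for baseline characteristics of the intention-to-treat population split by drop-out status.

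**The concern.** A safety comparison should include everyone exposed, whether or not they later gave an efficacy measurement. The section 4.1 set requires a glucose value about six months after the start, so a subject who has an event in the first weeks and then stops is outside it. The SAP expects more such losses in the water arm, so this rule would thin the safety comparison unevenly, and in the arm where water-balance problems are being watched for.

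The second issue concerns the primary result. Unequal loss is the setting in which missing at random is hardest to take on trust. The data set called imputed in section 5.6.2 does not help, because it fills covariates and not glucose. That leaves the scenario exercise in section 6.3. If its values, population and variance method are chosen after the data are seen, its result will carry little weight in either direction. Filling gaps could also be done with single fixed values treated as observed, which understates the variance.

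**Working it through.** **1. Comparing the two sets.** Section 4.1 needs V3 glucose plus V6 or V8 glucose. Section 5.7.3 needs V3 attendance. The difference is essentially the drop-outs defined in section 5.8: V3 attended, no later fasting glucose. It is not exactly that group. Someone without a valid fasting value at V3 but with one at V6 only would also fall outside section 4.1 without being a section 5.8 drop-out.

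**2. Reproducing the plan's sample size.** Inputs from SAP section 3.3: difference 0.14 mmol/L, SD 0.58, two-sided 5%, 80% power.
- Equal arms, standard two-sample calculation: 270 per group, 540 in total, as stated.
- At 46:54: 540 / (4 × 0.46 × 0.54) = 543.5, matching the stated 544.
- SE = 0.58 × √(1/250 + 1/294) = 0.0499; 0.14 / 0.0499 = 2.81; power 80%.

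**3. Net difference in omitted subjects.** Assume equal arms at V3 (1:1 allocation, balanced V2–V3 loss).
- 0.46 × 544 = 250; 0.54 × 544 = 294; difference 44.
- Rounding of the percentages: 544 × (0.535 − 0.465) = 38 to 544 × (0.545 − 0.455) = 49.
- Ratio of retention, water to control: 0.46 / 0.54 = 0.85.

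The 44 is the excess of water-arm over control leavers. Section 4.1 would omit all leavers in both arms, a number the documents do not state.

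**4. How far missing data could move the result (illustration only).** The Protocol (Sample size) anticipates drop-out of up to 20%. Assume all of it occurs after V3, with the 46:54 split.
- V3 attenders: 544 / 0.80 = 680, or 340 per arm.
- Water-arm loss: 1 − 250/340 = 26%. Control loss: 1 − 294/340 = 14%.
- If lost water-arm subjects had no benefit and lost controls resembled retained controls: 0.14 × (1 − 0.264) = 0.103; z = 0.103 / 0.0499 = 2.07, above 1.96.
- Loss at which z reaches 1.96: 1.96 × 0.0499 = 0.0978; 1 − 0.0978/0.14 = 30%.
- Shift from missing at random in lost water-arm subjects that brings z to 1.96: (0.14 − 0.0978) / 0.264 = 0.16 mmol/L.
- In the other direction, if lost controls were 0.14 mmol/L worse than missing at random predicts: 0.14 + 0.14 × 0.136 = 0.159.

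The SE is held fixed. Baseline adjustment and use of both visits would tend to lower it; fewer 12-month values and imputation variance would raise it.

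**5. Why the variance method matters.** With the same 340 per arm, suppose each gap were filled with one fixed value at its arm's mean and analysed as observed.
- Naive SE = 0.58 × √((0.736 + 0.864)/340) = 0.0398, against 0.0499: a ratio of 0.80.
- The critical value becomes 1.96 × 0.80 = 1.56, so a nominal 5% test runs at about 12%.

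This is a one-visit simplification. Section 6.3 does not say it would be done this way, but does not exclude it.

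**The case against.** The strongest reply on safety is that section 5.7.3 is the dedicated section and commits to reporting events for all V3 attenders. The section 4.1 sentence is a general line in a set definition, and all events are recorded in the eCRF in any case. This largely stands. A reader might infer that early leavers' events will vanish; the documents do not support that. At worst they are missing from one of two possible between-arm comparisons, and the defect is that the SAP does not say which comparison counts. Nor do the documents show that sodium and osmolality results themselves enter the comparison: out-of-range values count as adverse events in the Protocol, but section 5.7.3 reports events as diagnosis codes.

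On missing data, the reply is that section 6.3 already promises pessimistic scenarios because of unequal drop-out, and that the primary analysis would not change. Both are true. It would be wrong to say that no check exists. What stands is that the check has no content fixed in advance.

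Two further inferences fail. The 46:54 figure is the make-up of the final sample, not retention of 46% and 54%. And the figures do not show that plausible losses overturn the result: under the no-benefit assumption, reversal needs more than about 30% of the water arm missing. That exceeds the 26% implied by the Protocol's 20%, unless subjects with V6 but no V8 add to 12-month missingness.

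**Conclusion.** Both parts hold and should be fixed, though neither threatens the design. The SAP gives two populations for one safety comparison. Following section 4.1 would leave out a net excess of about 44 water-arm subjects (38 to 49), assuming equal arms at V3 and a final sample of 544, which the SAP gives as a minimum. The effect on event rates cannot be sized, because no rate for leavers is given.

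The missing-data check is announced but unspecified. The case for specifying it rests on expected unequal loss and on a tipping shift, 0.16 mmol/L in the illustration, close to the design effect of 0.14. It does not rest on any showing that the conclusion would reverse. The direction of bias is open, and the z-values assume an observed effect of exactly 0.14.

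The section 5.8 table is a minor wording fault: no drop-out as defined there can belong to the intention-to-treat set. It affects no estimate.

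**What to change.** 1. Delete adverse events and serious adverse events from the intention-to-treat definition in SAP section 4.1, so that the all-attended-V3 set of section 5.7.3 governs both reporting and comparison.
2. Before database lock, replace the post-hoc paragraph of section 6.3 with a pre-specified sensitivity analysis of the 12-month contrast in all V3 attenders, including those with V6 but no V8. Use either a delta-adjusted tipping-point series or control-based multiple imputation, state the deltas for each arm, and pool by Rubin's rule with the PROC MI and PROC MIANALYZE already named in section 4.1.
3. Minor: draw the section 5.8 baseline table from all V3 attenders.

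The cost is two wording changes, one rewritten paragraph and a few extra SAS runs. No new data are needed and the primary analysis is untouched. The downside is that the deltas must be argued in advance and the sensitivity estimates may be less precise.

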#### Per protocol

The key protocol deviation that can influence the therapy tested (increased water intake vs control) is that the study subjects do not adhere to the assigned therapy (do not increase water intake in active group / increase water intake in control group). Generally, unless a study treatment is directly administered by study personnel (for example short-term intravenous pharmacological infusions in the inpatient setting) it is impossible to fully control the adherence to the study therapies as study subjects administer the study therapies themselves at home. This limitation is thus the same as in randomized drug trials, where “pill counting” is the most common way to assess compliance/adherence. Whereas the “intention to treat” analysis, which is the primary method, tests if the assigned therapy works regardless of adherence, the secondary “per protocol” analyses will take into account the best available measure of compliance to the current therapy, which is changes of 24-urine measures during follow-up in comparison with baseline. In these per protocol analyses, we will exclude study subjects who, based on values of their 24-hour urine, show indications of poor compliance.

The exclusion of patients let to define the Per-Protocol Set will be based on the urine volume and concentration. These parameters will be considered as the main protocol deviation criteria. Cut-offs for inclusion in the per protocol analysis are at least one of the two criteria below met for 24h UOsm OR UVol:

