strongly predicts new onset type 2 diabetes independently of all other diabetes risk factors (8), a finding that has later been replicated by other groups in large independent cohorts (Diabetologia 2012;55:1963-70; JCEM 2015;100:3332-9). Healthy subjects in the top quartile of copeptin (corresponding to plasma concentration of copeptin of >6.1 pmol/L in women and >10.7 pmol/L in men) had a 3-4 fold multivariate adjusted risk of developing diabetes as compared to subjects in the lowest quartile of copeptin (8). Just like Cushing’s syndrome patients, subjects with high VP concentration are not only susceptible to diabetes. We showed that they are more likely to suffer from all components of the metabolic syndrome; i.e. abdominal obesity, insulin resistance, hypertension (6-8) and that high VP is an independent risk factor for CVD and premature mortality (1-2). As a low water intake is the most likely cause of elevated VP levels, we tested in animals if high water intake leads to suppression of VP and amelioration of dysmetabolic phenotypes. Interestingly, whereas rats with high VP had deteriorated glucose tolerance, high water intake suppressed VP, ameliorated insulin resistance and markedly prevented hepatic steatosis, one of the hallmarks of the metabolic syndrome (4). These data support a causal relationship between high VP, diabetes and metabolic syndrome, and suggest that water supplementation in humans with high VP may reduce the risk of diabetes and cardiometabolic risk.

PROJECT DESIGN (PICO)

Population: *We previously showed that subjects with high VP (copeptin of >6.1 pmol/L in women and >10.7 pmol/L in men), which corresponds to 25% of the population aged 20-75y, has 3-4 times elevated risk for diabetes development, i.e. a magnitude of risk that is similar to that of obesity, and a doubled risk of CVD mortality. In addition, this high VP target group has a urine osmolality of >600 mosm/kg water, i.e. concentrated urine concordant with a low water intake.*

FIGURE 1. Flowchart of screening and inclusion process

Inclusion criteria will be provision of informed consent, age 20-75 years with high plasma concentration of VP (plasma concentration of copeptin of >6.1 pmol/L in women and >10.7 pmol/L in men) and 24-hour urine osmolality >600 mosm/kg water.

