Exclusion criteria will be 24-hour urine volume \geq 1.5 L, pregnancy or breastfeeding, plasma sodium <135 mM, use of diuretics, lithium or SSRI drugs, chronic kidney disease (eGFR<30mL/min), heart failure, inflammatory bowel disease, type 1 diabetes or type 2 diabetes treated with insulin and vulnerable subjects (subjects with legal guardian, with loss of personal liberty).

Study subjects will be recruited from ongoing population studies in the Scania region encompassing altogether 20 000 individuals within the current age span: The Swedish CardioPulmonary Imaging Study (SCAPIS) (n=6000) (<https://www.hjart-lungfonden.se/scapis>), BIG3 (n=4000) (http://www.skane.se/webbplatser/fou_centrum_skane/big3/), EpiHealth (n=9000) (<https://www.epihealth.se/>) and the Malmö Offspring Study (n=1000) (<http://www.med.lu.se/mos>). Copeptin will be measured in -80 degree frozen plasma samples from these four studies. Assuming that the prevalence of having plasma copeptin concentration of >6.1 pmol/L in women and >10.7 pmol/L in men will be approximately 25%, this will give us a pool of candidates for participation in the intervention trial of approximately 6500 individuals. If fewer than expected subjects fulfilling the criteria for inclusion will be generated from this source of inclusion, we will invite employees of the City of Malmö and employees of Skåne University Hospital who are 20-75 years of age to undergo a fasting plasma determination of copeptin. If the plasma concentration of copeptin is >6.1 pmol/L in women and >10.7 pmol/L in men, subjects will enter the same procedure to further test inclusion and exclusion criteria as participants of the population studies (detailed above). As a third source of recruitment, advertisements in local press will be used to invite subjects from the population aged 20-75 years to be tested for plasma copeptin followed by an identical test of inclusion and exclusion criteria as described above.

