**Delta 24h UOsm (Baseline vs. 3 months, 6 months, 9 months and 12 months):**

- Control Group: Those with a decrease in delta 24h UOsm not greater than 25% from baseline.
- Intervention group: Those with a decrease in delta 24h UOsm of at least 50% from baseline.

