**OR Delta 24h UVol (Baseline vs. 3 months, 6 months, 9 months and 12 months):**

- Control Group: Those with an increase in delta 24h UVol not greater than 500 mL from baseline.
- Intervention group: Those with an increase in delta 24h UVol of at least 1000 mL from baseline.

Furthermore, all individuals attending a clinic study visit (V3, V6 or V8) in a non-fasted state will be excluded from the per protocol analyses. Some other protocol deviations let to exclude patients are detailed in Section 5.1.2

Missing data

Missing data on outcomes (i.e. change of fasting glucose and the secondary cardiometabolic measures) will not be imputed, so subjects with missing data on outcome parameters will not be included in analysis of the respective outcome. For each of the outcomes, the maximum number of subjects will be included (e.g. if there are n=544 evaluable subjects for fasting glucose change, all of these will be included even if there are less evaluable subjects for any other cardiometabolic outcome parameter).

Given the randomized nature of the study, we will not perform any adjustments (which in turn can be affected by missing data on the covariates adjusted for) with three exceptions: (1) As detailed in “statistics” we will include adjustment for the baseline value of the outcome parameter in question (e.g. the change of glucose outcome will be adjusted for the baseline value of glucose). The motif of this adjustment is to minimize bias related to regression towards the mean. (2) As the randomization is stratified by sex, this covariate will be included in all outcome analyses. (3) If clinically significant/meaningful treatment group differences appear in baseline values of age, BMI or diabetes status in any outcome analysis, we will add a sensitivity outcome analysis in which we adjust for such baseline differences. Any missing values for these covariates will be imputed to obtain the same number of evaluable subjects in non-adjusted and adjusted analyses. The technique we propose is Multiple Imputation by Chained Equations (MICE) with subsequent application of Rubin’s rule to combine results from different imputations. We will base the analyses on 20-30 imputed data sets. For this analysis we will use SAS PROC MI in combination with PROC MIXED/PROC GLM and PROC MIANALYZE.

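### The per-protocol rule keeps a control who meets either urine limit, which leaves the 25% osmolality limit with almost no effect and contradicts the stated aim of excluding poor compliers

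*SAP*

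**What the plan says.** SAP 4.1 (Per protocol) gives the purpose: "we will exclude study subjects who, based on values of their 24-hour urine, show indications of poor compliance". It then sets the rule: "Cut-offs for inclusion in the per protocol analysis are at least one of the two criteria below met for 24h UOsm OR UVol". The OR is repeated at the head of the volume criteria.

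- Control, osmolality: "Control Group: Those with a decrease in delta 24h UOsm not greater than 25% from baseline".
- Control, volume: "Control Group: Those with an increase in delta 24h UVol not greater than 500 mL from baseline".
- Intervention, osmolality: "Intervention group: Those with a decrease in delta 24h UOsm of at least 50% from baseline".
- Intervention, volume: "Intervention group: Those with an increase in delta 24h UVol of at least 1000 mL from baseline".

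Both pairs list the 3-, 6-, 9- and 12-month visits without saying whether any, all, the last or the mean must qualify. SAP 5.1.2 only refers back to 4.1. SAP 5.4 tabulates osmolality and volume at 6 and 12 months, but its derivation text names urine volume alone as the per-protocol compliance measure. No section gives a reason for OR or ranks the two measures.

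The per-protocol set is used for the primary outcome (5.6), the secondary outcomes (5.7.1) and all subgroups (6.6). SAP 4.1 makes intention to treat the primary method.

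**The concern.** The intervention criteria are floors: reaching either one is evidence that the subject drank more. The control criteria are ceilings: breaking either one is evidence that the subject drank more. Joining floors by OR is a lenient but coherent choice. Joining ceilings by OR means that a sign of non-adherence on one measure is overruled by the other.

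The per-protocol analysis is there to show the effect when water intake really differs between arms. If controls who diluted their urine remain, that contrast is blurred, and a per-protocol result close to the ITT result becomes hard to interpret. As the visits are not combined by any stated rule, membership cannot be programmed from the text and could be settled after results are known.

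**Working it through.** The documents state no figure for the size or error rate of this set, so there is none to reproduce. The check is logic plus a mass balance.

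**Inputs.** The four cut-offs are from SAP 4.1. The Protocol excludes a 24-hour volume of 1.5 L or more and requires "24-hour urine osmolality >600 mosm/kg water"; SAP 3.2 writes the volume limit as at most 1.5 L. No lower volume limit is given. I take the baseline value to be the collection used for eligibility, which Protocol Table 1 places at the inclusion visit.

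**1. Logic alone.** A control with a rise of 500 mL or less is kept whatever the osmolality fall. This needs no assumption.

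**2. Redundancy at constant solute.** Let V0 be baseline volume, dV the rise, and r the follow-up to baseline ratio of daily solute (volume × osmolality). The fall is f = 1 − r·V0/(V0 + dV). With r = 1, f = 25% gives dV = V0/3, and dV = 500 mL gives f = 500/(V0 + 500).

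| V0 (mL) | Rise at a 25% fall (mL) | Fall at +500 mL |
|---|---|---|
| 500 | 167 | 50% |
| 600 | 200 | 45% |
| 750 | 250 | 40% |
| 1000 | 333 | 33% |
| 1250 | 417 | 29% |
| 1400 | 467 | 26% |

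Since V0 is below 1500 mL, V0/3 is below 500 mL. Every control who meets the osmolality limit already meets the volume limit, so the OR set equals the volume-only set.

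**3. If measured solute varies.** OR then also admits controls above 500 mL when f ≤ 25%, that is, r ≥ 0.75(1 + dV/V0). At V0 = 1000 mL and dV = 600 mL this is r ≥ 0.75 × 1.6 = 1.2. OR is then looser than volume alone.

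**4. Overlap of the arms.** At r = 1 a control qualifies if dV ≤ 500 mL, and an intervention subject if dV is at least the smaller of V0 and 1000 mL. Both can hold only if V0 ≤ 500 mL. Otherwise solute must change, by one of two routes:

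- Fall ≥ 50% with rise ≤ 500 mL needs r ≤ 0.5(1 + 500/V0): 0.83, 0.75 and 0.68 at V0 = 750, 1000 and 1400 mL. Example: 1000 mL at 800 mosm/kg becomes 1500 mL at 400 (fall 50%, rise 500 mL, r = 0.75).
- Fall ≤ 25% with rise ≥ 1000 mL needs r ≥ 0.75(1 + 1000/V0): 1.50 and 1.29 at 1000 and 1400 mL. Example: 1400 mL at 700 mosm/kg becomes 2400 mL at 530 (fall 24.3%, rise 1000 mL, r = 1.30).

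**5. Possible frequency, on assumed inputs only.** With V0 uniform on 0.5–1.5 L, volume change SD 300 mL and mean rise 0 to 1000 mL, a single collection counts as adherent in both arms in 0% of cases at constant solute. At a per-collection solute CV of 10%, 20% and 30% the share is 0.3–0.9%, 2.5–4.6% and 6.3–9.4%. Applied to a four-visit mean in subjects with no true change (inputs as in step 6), it is about 0–3%.

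**6. Effect of requiring both control limits.** Overlap becomes zero even if the intervention arm keeps OR, because a fall ≤ 25% excludes ≥ 50% and a rise ≤ 500 mL excludes ≥ 1000 mL. On the step 5 inputs, with a mean control rise of 300 mL and constant solute, retention is 75% under OR and 54% under both limits. The price is paid partly by adherent controls. In simulations of controls with no true change (assumed: true volume median 1.1 L, within-person CV 15–35% for volume and 10–20% for solute, one eligibility collection, four-visit mean), both limits exclude about 9–37% and OR about 1–15%. Other assumed variation widens these to about 8–47% and 0–25%.

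**The case against.** The strongest defence is that 24-hour collections are error-prone. An incomplete collection lowers measured volume but need not change concentration, so accepting either measure protects adherent subjects. Subjects are also selected on high osmolality and low volume, so control osmolality will drift down by regression to the mean with no change in drinking; a strict control rule would remove such people and add arm-specific, post-randomisation selection of its own. Both arguments stand as reasons to state the cost and keep the OR set as a sensitivity analysis. They do not rescue the present text, because the SAP gives no such rationale and its stated aim points the other way.

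A reader might infer three stronger things that the documents do not support:

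- **That the 25% limit can never have any effect.** Redundancy needs constant measured solute. When solute varies the osmolality criterion does act, but by admitting more controls.
- **That the arms overlap widely.** At constant solute this needs a baseline of 0.5 L or less, and the documents give no distribution of baseline volume.
- **That the trial's main result is at risk.** The ITT analysis does not use this rule.

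It is also true that any per-protocol set loses the protection of randomisation, so that by itself is no special fault here. Nor is it one that an intervention subject with a 0.6 L baseline qualifies at about +600 mL: the SAP gives the 50% fall equal standing with the 1000 mL rise.

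**Conclusion.** The concern holds as a defect in a secondary analysis. By logic alone, the rule keeps controls whose osmolality fell by any amount provided volume rose by no more than 500 mL, against the SAP's own aim. Given roughly constant solute and baseline volume below 1.5 L, the 25% limit is redundant; given variable solute, the rule is looser still. Adherence in both arms by the same urine change is possible but probably confined to a few percent; that figure rests on assumed inputs. The likely effect is a diluted and hard-to-interpret per-protocol contrast for the primary outcome, secondary outcomes and subgroups. The missing visit rule and the mismatch between SAP 4.1 and 5.4 are firm gaps that rest on no assumption.

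**What to change.** In SAP 4.1:

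1. Require controls to meet both limits; the intervention arm can keep OR. Alternatively, name one urine measure in advance for both arms. Either removes the overlap, but volume alone would drop the osmolality limit openly rather than make it bind.
2. Apply the criteria to the mean of the available 3-, 6-, 9- and 12-month collections.
3. Reconcile the volume-only wording in 5.4 with 4.1.
4. Keep the current OR set as a sensitivity analysis, with numbers excluded by arm and by criterion.

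This is a wording change on data already collected. The cost is a smaller control per-protocol set, including the loss of some adherent controls through regression to the mean. Requiring both criteria in the intervention arm as well is unnecessary and expensive: on the step 5 inputs at a mean rise of 1000 mL, adherent intervention subjects fall from 64–71% to 31–36%.

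An instrumental-variable estimate (randomised arm as instrument, change in urine volume as exposure) is optional. If reported, it must state the assumption that assignment affects glucose only through urine volume, since SAP 3.1.3 itself names diet, including sweetened drinks, as a possible mediator.
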